# LIST OF ABBREVIATIONS

BWSBody weight supportCFRCode of Federal RegulationsCMSAN(Mayo Clinic) Center for Multiple Sclerosis and Autoimmune NeurologyCRFCase Report FormDSMBData and Safety Monitoring BoardEDSSExpanded Disability Severity ScaleEMGElectromyographyESEpidural electrical spinal stimulationFDAFood and Drug AdministrationGCPGood Clinical PracticeHIPAAHealth Insurance Portability and Accountability ActHRPOHuman Research Protection OfficeIDEInvestigational Device ExemptionIRBInstitutional Review BoardMASModified Ashworth ScaleMSMultiple sclerosisMSQLIMS Quality of Life InventoryNSTEP-MSNeuroStimulation Therapy to Alleviate Symptoms of Progressive MSPHIProtected Health InformationPISpinal Cord InjurySOPStandard Operating ProcedureTUGTimed up and GoUADEUnanticipated Adverse Device Effect	AE	Adverse Event/Adverse Experience
CFRCode of Federal RegulationsCMSAN(Mayo Clinic) Center for Multiple Sclerosis and Autoimmune NeurologyCRFCase Report FormDSMBData and Safety Monitoring BoardEDSSExpanded Disability Severity ScaleEMGElectromyographyESEpidural electrical spinal stimulationFDAFood and Drug AdministrationGCPGood Clinical PracticeHIPAAHealth Insurance Portability and Accountability ActHRPOHuman Research Protection OfficeIDEInvestigational Device ExemptionIRBInstitutional Review BoardMASModified Ashworth ScaleMSMultiple sclerosisMSQLIMS Quality of Life InventoryNSTEP-MSNeuroStimulation Therapy to Alleviate Symptoms of Progressive MSPHIProtected Health InformationPISpinal Cord InjurySOPStandard Operating ProcedureTUGTimed up and Go	BWS	Body weight support
and Autoimmune NeurologyCRFCase Report FormDSMBData and Safety Monitoring BoardEDSSExpanded Disability Severity ScaleEMGElectromyographyESEpidural electrical spinal stimulationFDAFood and Drug AdministrationGCPGood Clinical PracticeHIPAAHealth Insurance Portability and Accountability ActHRPOHuman Research Protection OfficeIDEInvestigational Device ExemptionIRBInstitutional Review BoardMASModified Ashworth ScaleMSMultiple sclerosisMSQLIMS Quality of Life InventoryNSTEP-MSNeuroStimulation Therapy to Alleviate Symptoms of Progressive MSPHIProtected Health InformationPISpinal Cord InjurySOPStandard Operating ProcedureTUGTimed up and Go	CFR	Code of Federal Regulations
and Autoimmune NeurologyCRFCase Report FormDSMBData and Safety Monitoring BoardEDSSExpanded Disability Severity ScaleEMGElectromyographyESEpidural electrical spinal stimulationFDAFood and Drug AdministrationGCPGood Clinical PracticeHIPAAHealth Insurance Portability and Accountability ActHRPOHuman Research Protection OfficeIDEInvestigational Device ExemptionIRBInstitutional Review BoardMASModified Ashworth ScaleMSMultiple sclerosisMSQLIMS Quality of Life InventoryNSTEP-MSNeuroStimulation Therapy to Alleviate Symptoms of Progressive MSPHIProtected Health InformationPISpinal Cord InjurySOPStandard Operating ProcedureTUGTimed up and Go	CMSAN	(Mayo Clinic) Center for Multiple Sclerosis
DSMBData and Safety Monitoring BoardEDSSExpanded Disability Severity ScaleEMGElectromyographyESEpidural electrical spinal stimulationFDAFood and Drug AdministrationGCPGood Clinical PracticeHIPAAHealth Insurance Portability and Accountability ActHRPOHuman Research Protection OfficeIDEInvestigational Device ExemptionIRBInstitutional Review BoardMASModified Ashworth ScaleMSMultiple sclerosisMSQLIMS Quality of Life InventoryNSTEP-MSNeuroStimulation Therapy to Alleviate Symptoms of Progressive MSPHIProtected Health InformationPISpinal Cord InjurySOPStandard Operating ProcedureTUGTimed up and Go		and Autoimmune Neurology
EDSSExpanded Disability Severity ScaleEMGElectromyographyESEpidural electrical spinal stimulationFDAFood and Drug AdministrationGCPGood Clinical PracticeHIPAAHealth Insurance Portability and Accountability ActHRPOHuman Research Protection OfficeIDEInvestigational Device ExemptionIRBInstitutional Review BoardMASModified Ashworth ScaleMSMultiple sclerosisMSQLIMS Quality of Life InventoryNSTEP-MSNeuroStimulation Therapy to Alleviate Symptoms of Progressive MSPHIProtected Health InformationPISerious Adverse Event/Serious Adverse ExperienceSCISpinal Cord InjurySOPStandard Operating ProcedureTUGTimed up and Go	CRF	Case Report Form
EMGElectromyographyESEpidural electrical spinal stimulationFDAFood and Drug AdministrationGCPGood Clinical PracticeHIPAAHealth Insurance Portability and Accountability ActHRPOHuman Research Protection OfficeIDEInvestigational Device ExemptionIRBInstitutional Review BoardMASModified Ashworth ScaleMSMultiple sclerosisMSQLIMS Quality of Life InventoryNSTEP-MSNeuroStimulation Therapy to Alleviate Symptoms of Progressive MSPHIProtected Health InformationPISerious Adverse Event/Serious Adverse ExperienceSCISpinal Cord InjurySOPStandard Operating ProcedureTUGTimed up and Go	DSMB	Data and Safety Monitoring Board
ESEpidural electrical spinal stimulationFDAFood and Drug AdministrationGCPGood Clinical PracticeHIPAAHealth Insurance Portability and Accountability ActHRPOHuman Research Protection OfficeIDEInvestigational Device ExemptionIRBInstitutional Review BoardMASModified Ashworth ScaleMSMultiple sclerosisMSQLIMS Quality of Life InventoryNSTEP-MSNeuroStimulation Therapy to Alleviate Symptoms of Progressive MSPHIProtected Health InformationPISerious Adverse Event/Serious Adverse ExperienceSCISpinal Cord InjurySOPStandard Operating ProcedureTUGTimed up and Go	EDSS	Expanded Disability Severity Scale
FDAFood and Drug AdministrationGCPGood Clinical PracticeHIPAAHealth Insurance Portability and Accountability ActHRPOHuman Research Protection OfficeIDEInvestigational Device ExemptionIRBInstitutional Review BoardMASModified Ashworth ScaleMSMultiple sclerosisMSQLIMS Quality of Life InventoryNSTEP-MSNeuroStimulation Therapy to Alleviate Symptoms of Progressive MSPHIProtected Health InformationPISerious Adverse Event/Serious Adverse ExperienceSCISpinal Cord InjurySOPStandard Operating ProcedureTUGTimed up and Go	EMG	Electromyography
GCPGood Clinical PracticeHIPAAHealth Insurance Portability and Accountability ActHRPOHuman Research Protection OfficeIDEInvestigational Device ExemptionIRBInstitutional Review BoardMASModified Ashworth ScaleMSMultiple sclerosisMSQLIMS Quality of Life InventoryNSTEP-MSNeuroStimulation Therapy to Alleviate Symptoms of Progressive MSPHIProtected Health InformationPISerious Adverse Event/Serious Adverse ExperienceSCISpinal Cord InjurySOPStandard Operating ProcedureTUGTimed up and Go	ES	Epidural electrical spinal stimulation
HIPAAHealth Insurance Portability and Accountability ActHRPOHuman Research Protection OfficeIDEInvestigational Device ExemptionIRBInstitutional Review BoardMASModified Ashworth ScaleMSMultiple sclerosisMSQLIMS Quality of Life InventoryNSTEP-MSNeuroStimulation Therapy to Alleviate Symptoms of Progressive MSPHIProtected Health InformationPISerious Adverse Event/Serious Adverse ExperienceSCISpinal Cord InjurySOPStandard Operating ProcedureTUGTimed up and Go	FDA	Food and Drug Administration
HRPOHuman Research Protection OfficeIDEInvestigational Device ExemptionIRBInstitutional Review BoardMASModified Ashworth ScaleMSMultiple sclerosisMSQLIMS Quality of Life InventoryNSTEP-MSNeuroStimulation Therapy to Alleviate Symptoms of Progressive MSPHIProtected Health InformationPIPrincipal InvestigatorSAESerious Adverse Event/Serious Adverse ExperienceSCISpinal Cord InjurySOPStandard Operating ProcedureTUGTimed up and Go	GCP	Good Clinical Practice
IDEInvestigational Device ExemptionIRBInstitutional Review BoardMASModified Ashworth ScaleMSMultiple sclerosisMSQLIMS Quality of Life InventoryNSTEP-MSNeuroStimulation Therapy to Alleviate Symptoms of Progressive MSPHIProtected Health InformationPIPrincipal InvestigatorSAESerious Adverse Event/Serious Adverse ExperienceSCISpinal Cord InjurySOPStandard Operating ProcedureTUGTimed up and Go	HIPAA	Health Insurance Portability and Accountability Act
IRBInstitutional Review BoardMASModified Ashworth ScaleMSMultiple sclerosisMSQLIMS Quality of Life InventoryNSTEP-MSNeuroStimulation Therapy to Alleviate Symptoms of Progressive MSPHIProtected Health InformationPIPrincipal InvestigatorSAESerious Adverse Event/Serious Adverse ExperienceSCISpinal Cord InjurySOPStandard Operating ProcedureTUGTimed up and Go	HRPO	Human Research Protection Office
MASModified Ashworth ScaleMSMultiple sclerosisMSQLIMS Quality of Life InventoryNSTEP-MSNeuroStimulation Therapy to Alleviate Symptoms of Progressive MSPHIProtected Health InformationPIPrincipal InvestigatorSAESerious Adverse Event/Serious Adverse ExperienceSCISpinal Cord InjurySOPStandard Operating ProcedureTUGTimed up and Go	IDE	Investigational Device Exemption
MSMultiple sclerosisMSQLIMS Quality of Life InventoryNSTEP-MSNeuroStimulation Therapy to Alleviate Symptoms of Progressive MSPHIProtected Health InformationPIPrincipal InvestigatorSAESerious Adverse Event/Serious Adverse ExperienceSCISpinal Cord InjurySOPStandard Operating ProcedureTUGTimed up and Go	IRB	Institutional Review Board
MSQLIMS Quality of Life InventoryNSTEP-MSNeuroStimulation Therapy to Alleviate Symptoms of Progressive MSPHIProtected Health InformationPIPrincipal InvestigatorSAESerious Adverse Event/Serious Adverse ExperienceSCISpinal Cord InjurySOPStandard Operating ProcedureTUGTimed up and Go	MAS	Modified Ashworth Scale
NSTEP-MSNeuroStimulation Therapy to Alleviate Symptoms of Progressive MSPHIProtected Health InformationPIPrincipal InvestigatorSAESerious Adverse Event/Serious Adverse ExperienceSCISpinal Cord InjurySOPStandard Operating ProcedureTUGTimed up and Go	MS	Multiple sclerosis
Progressive MSPHIProtected Health InformationPIPrincipal InvestigatorSAESerious Adverse Event/Serious Adverse ExperienceSCISpinal Cord InjurySOPStandard Operating ProcedureTUGTimed up and Go	MSQLI	MS Quality of Life Inventory
PHIProtected Health InformationPIPrincipal InvestigatorSAESerious Adverse Event/Serious Adverse ExperienceSCISpinal Cord InjurySOPStandard Operating ProcedureTUGTimed up and Go	NSTEP-MS	NeuroStimulation Therapy to Alleviate Symptoms of
PIPrincipal InvestigatorSAESerious Adverse Event/Serious Adverse ExperienceSCISpinal Cord InjurySOPStandard Operating ProcedureTUGTimed up and Go		Progressive MS
SAESerious Adverse Event/Serious Adverse ExperienceSCISpinal Cord InjurySOPStandard Operating ProcedureTUGTimed up and Go	PHI	Protected Health Information
SCISpinal Cord InjurySOPStandard Operating ProcedureTUGTimed up and Go	PI	Principal Investigator
SOPStandard Operating ProcedureTUGTimed up and Go	SAE	Serious Adverse Event/Serious Adverse Experience
TUG Timed up and Go	SCI	
	SOP	1 0
UADE Unanticipated Adverse Device Effect		Timed up and Go
	UADE	Unanticipated Adverse Device Effect

# **Study Summary**

Title	A Pilot Study to Explore the Use of Percutaneous Spinal Stimulation in Participants with Multiple Sclerosis
Running Title	ES in MS
IRB Protocol Number	23-003967
Phase	Pilot Study
Methodology	Prospective study
Overall Study Duration	3-year duration
Subject Participation Duration	Less than 2 months per subject
Objectives	
 
a) Evaluate the effectiveness of percutaneous ES and task-specific training in participants with Progressive MS to impact motor function and spasticity.
 
b) Investigate the potential of ES and task-specific training to impact non-motor spinal related dysfunction in the same participants.
 

Number of Subjects	10 subjects
Diagnosis and Main Inclusion Criteria	Multiple Sclerosis with EDSS of 6.5
Study Device	Abbott percutaneous trial lead for epidural neurostimulation (Model 3086) Ripple Nomad Neurostimulator Abbott clinician programmer, (Model 3874)
Duration of Exposure	All subjects will complete 1 month of temporary epidural spinal stimulation (ES) with task-specific training.
Reference therapy	The reference therapy is clinical rehabilitation with MS.
Statistical Methodology	Descriptive statistics will be used to describe stimulation-related outcomes. Repeated measures analyses of variance will be used to detect changes in outcomes pre- to post-ES and training.

# **1** Introduction

This document is a protocol for a human research study. This study will be carried out in accordance with the procedures described in this protocol, applicable United States government regulations and Mayo Clinic policies and procedures.

Up to 75% of patients with MS develop progressive MS, and there is no current treatment to halt clinical progression or axonal loss in patients with progressive MS. Progressive MS is

defined by a sustained clinical worsening, typically of walking difficulties, over more than 1 year in the absence of clinically detectable MS relapses or attacks (Thompson et al., 2018). Pathologically, it is characterized by axonal loss in the absence of inflammatory disease. Patients typically have progressive difficulty walking with associated leg spasticity and urinary, bowel and sexual dysfunction.

Like MS, there is no cure for traumatic injury of the spinal cord which results in lifelong impairment of autonomic, sensory, and motor functions in regions of the body that are distal to the damaged areas of the spinal cord. In response to the complete lack of available therapies to restore volitionally-controlled lower extremity motor function, we recently conducted a pilot-phase clinical trial of epidural spinal electrical stimulation (ES) in combination with task-specific training; ES consists of an implanted stimulator and electrode array placed over the dura mater on the dorsal aspect of the spinal cord. ES with task-specific training resulted in unprecedented outcomes, such as restoration of standing and walking in humans previously diagnosed with complete paralysis of their lower extremities due to a traumatic spinal cord injury (SCI) that occurred several years prior (M. Gill et al., 2020; M. L. Gill et al., 2018; Grahn et al., 2017). Likewise, other research teams have shown remarkable improvements in spinal stimulation-enabled motor functions that are retained after study participation in individuals with incomplete paralysis (Wagner et al., 2018). Herein, we propose leveraging the knowledge and expertise gained during our previous, and active, clinical trials of ES in participants with paralysis to determine the translational potential of epidural spinal electrical stimulation (ES) for improvement of motor function and spasticity in patients with myelopathy due to progressive multiple sclerosis (MS). The following are key aspects of the proposed work:

- The proposed research is a pilot study which will explore epidural spinal stimulation (ES) in combination with task-specific training to improve lower limb function in 10 participants with Progressive MS.
- We will temporarily implant percutaneous ES leads through the skin overlying the lumbosacral enlargement and remove the leads following the 4-week study.
- Participants will serve as their own control via a comparison of pre- and poststimulation outcomes and outcome metrics captured during ES and when ES is off.
- Safety will be continuously evaluated during the 4-week stimulation and task specific training period, and during a post lead removal neurologist visit.
- The percutaneous leads are currently used clinically and are approved for patients with low back pain; use in participants with MS will be possible under an FDA IDE.

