# 3 Study Design

# 3.1 General Design

This is a pilot study that will include a total of 10 subjects with Progressive MS (EDSS 6.5). All subjects will complete 1 month of ES and task-specific training. Expected duration of subject participation is less than 2 months. Baseline assessments will be obtained prior to implantation and post-stimulation assessments will be obtained prior to explantation, with stimulation on and off.

SCREENING	BASELINE	STIMULATION	POST- STIMULATION	
	Baseline Assessments	Minimum 12 Sessions	End Assessments	
Assessment of Inclusion/Exclusion criteria by study team	Clinical, Electromyography, Movement Assessments& Surveys	Stimulation + Task- Specific Training	Clinical, Electromyography, Movement Assessments & Surveys	STUDY END
	No Stim	Percutaneous Stimulation	Stim on/Stim off	
l-month pre- enrollment	Week 0-1	Weeks 1-4	Week 4-5	

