# 6 Study Procedures

# 6.1 Screening

Subjects will complete a variety of assessments and procedures to determine their enrollment eligibility. When possible, eligible subjects will have their screening data used as baseline data collection. The following tests/activities will be performed to determine eligibility based on the inclusion/exclusion criteria listed in this document.

- Review of available medical records
- Neurology and Physical Medicine and Rehabilitation clinical exams
- EDSS score evaluation
- Pregnancy test
- Spasticity examination
- Evaluation of rehabilitation task ability and range of motion of impaired joints
- Spine MRI
- Body weight

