#### **Outcome Measures** 6.4

The following outcome measures will be collected with tests occurring over an approximately one-week period of time for each time point. Photographic and video images will be recorded throughout the study but will not be shown to anyone outside the study team without the subject's written consent.

		Pre/ No Stim	Stimulation + Task-specific Training			Post/ Stim ON and OFF	
Outcomes	Specific Measure	wk 0	wk 1	wk 2	wk 3	wk 4	wk 4/5
	Primary						
Gait Analysis	EMG, Kinematics, Kinetics	Χ					X
Voluntary Movement	EMG, Kinematics	Χ	Χ			Χ	X
Spasticity	MAS, Pendulum Test	Χ					Χ
Secondary							
Functinal Mobility	TUG	Χ					X
MS Quality of Life Inventory	MSQLI	Χ					X

Aim 1 will quantify the effect of ES and task-specific training on lower extremity motor function in individuals with severe lower extremity motor disability due to progressive MS using the primary outcomes of kinematics (movement), kinetics (forces), and electromyography (muscle activity, EMG) collected during gait, standing, and side lying motor tasks. Data will be reduced and summarized using standard biomechanical approaches, to quantify gait rhythm, lower extremity joint and body center of mass ranges of motion (during gait, standing, and side lying), and timing of muscle activations and ground reaction force peaks. Secondary outcomes include functional mobility assessments utilizing motion capture data, as well as the Timed Up and Go (TUG) test. Safety and tolerability will be assessed while monitoring vital signs and stimulation responsiveness during daily sessions and testing dates.

Aim 2 will determine the impact of ES and task-specific training on non-motor spinal related dysfunction in individuals with severe lower extremity motor disability due to progressive MS using the primary outcomes of the qualitative pendulum test (Smith et al., 2000) and the Modified Ashworth Scale to describe spasticity levels. Secondary outcomes will include the MS Quality of Life inventory that includes questions about bowel, bladder and sexual function, quality of life and pain, among others.

Aim 3 will be an *exploratory aim* to collect electrophysiological and biomarker data that may help us gain a mechanistic understanding of findings in Aims 1 and 2. To assess the Page 20 of 33 [name].

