# 7 Statistical Plan

# 7.1 Sample Size Determination

Due to the pilot phase of this study, no formal power calculations were performed for this proposal. The number of subjects was selected based on budgetary, space, and personnel time constraints. Ten participants (five males; five female) will be enrolled to complete this study, depending on need for contingency subjects. Participants will receive 4 weeks of ES and serve as their own control.

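### The modelled pre/post effect rests on one pre-treatment reading, which may be the screening value, so retest, drift and selection effects in either direction fall inside what 7.2 labels the ES treatment effect

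*Combined protocol and SAP*

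**What the plan says.** Section 1 (key aspects) bases the design on within-person comparison: "Participants will serve as their own control via a comparison of pre- and poststimulation outcomes". The same sentence adds a second contrast, "outcome metrics captured during ES and when ES is off". Section 7.1 repeats the principle: "Participants will receive 4 weeks of ES and serve as their own control".

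On timing, section 3.1 states: "Baseline assessments will be obtained prior to implantation and post-stimulation assessments will be obtained prior to explantation, with stimulation on and off". The schema there puts screening at one month before enrolment, baseline at week 0-1, stimulation at weeks 1-4 and the end assessments at week 4-5. Both schedule tables (under Secondary Study Endpoints and in 6.4) have one pre-treatment column, week 0, for every outcome. The extra voluntary-movement readings at weeks 1 and 4 fall in the stimulation period. Section 6.4 describes a time point as one battery: "The following outcome measures will be collected with tests occurring over an approximately one-week period of time for each time point". No repeat baseline is hidden there.

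Section 6.1 lists a spasticity examination and an evaluation of rehabilitation tasks at screening, but not TUG, the MS Quality of Life Inventory (MSQLI) or gait analysis. It then says: "When possible, eligible subjects will have their screening data used as baseline data collection".

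Section 7.2 fits a linear regression of the post value on the baseline value and reports the result as a treatment effect of ES. The Study Summary names repeated measures ANOVA, also pre to post. For stimulation on and off, 7.2 plans correlations only.

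**The concern.** With one group and one pre-treatment reading, nothing in the data shows what a second reading would have been without ES and training. TUG depends on effort and practice, MAS on the rater and MSQLI on self-report, and section 5.7 leaves the study unblinded. A shift that would have occurred on retest alone is therefore reported as an effect.

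Section 6.1 makes this worse in two ways. Where a screening value replaces the week-0 reading, the baseline can be up to about a month older for some participants than for others, and no rule says when this happens. For MAS, the screening value may also be the one used to apply the grade-4 exclusion in 4.2, so the baseline is then a reading on which participants were selected.

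At stake are the wording of the main result and the figures handed on to future studies. Section 7.2 intends the effect and variance estimates to inform later sample sizes.

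**Working it through.** **Plan's own figure.** There is none to reproduce. Section 7.1 says "no formal power calculations were performed for this proposal", and no alpha, effect or SD is given. From the documents: n = 10 ("Ten participants (five males; five female) will be enrolled to complete this study"), one group, one pre-treatment reading. Assumed: two-sided alpha 5%, test-retest correlation r of 0.7 to 0.9, and the size of any non-treatment shift.

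**1. What the regression estimates.** Fit post = a + b × (baseline − mean baseline) + error in one group. The estimate of a is the mean post value, so a minus the mean baseline is the mean change. That mean change equals treatment effect + retest shift + drift + selection effect. One number estimates the sum, and the covariate does not separate the parts. A simulation with n = 10, r = 0.8, no treatment effect and a shift of 0.3 between-person SD returned an average effect of 0.30 SD, nominally significant in 29% of runs.

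**2. Size, in SDs of the change score.** For a paired t-test, the noncentrality is d × √10 on 9 degrees of freedom.
- d = 0.3: noncentrality 0.95, rejection 13.6%.
- d = 0.5: noncentrality 1.58, rejection 29.3%.
- d = 0: rejection 5%.

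**3. Size, in between-person SDs.** The SD of the change is √(2(1 − r)) between-person SDs: 0.775, 0.632 and 0.447 for r = 0.7, 0.8 and 0.9.
- Shift 0.2 SD: d = 0.26, 0.32, 0.45; rejection 11%, 15%, 25%.
- Shift 0.3 SD: d = 0.39, 0.47, 0.67; rejection 20%, 27%, 47%.

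**4. Selection on MAS.** Treat MAS as roughly normal (it is ordinal, so this gives an order of magnitude only) and suppose the worst 5% to 20% are excluded on the screening reading. With that reading as baseline, the mean of post minus baseline is 0.01 to 0.11 SD over r = 0.9 to 0.7, toward apparent worsening. With a separate week-0 baseline it is about 0. With the mean of both readings it is about half.

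**5. Why the two readings should not be averaged.** Let drift be d per interval over two equal intervals, so the expected readings are 0, d and 2d. Post minus week 0 carries d. Post minus the mean of the first two carries 2d − 0.5d = 1.5d. Averaging gains precision but increases drift bias, and for MAS it keeps half the selection effect.

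**6. Why the untreated change should not drive a decision rule.** With no drift, no effect and equally correlated readings, the later of two successive changes is the larger in size about half the time. A rule that asks only whether the pre-post change exceeds the untreated change is therefore passed about 50% of the time under the null. The formal double difference, (post − week 0) − (week 0 − screening), does hold its level under steady drift (4.9% in simulation at 0.3 SD per interval, r = 0.8). But its standard error is √6/√2 = √3 times that of the simple change, and the effect detectable with 80% power goes from 0.63 to 1.09 SD (r = 0.8).

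**7. Precision of the untreated change.** The 95% half-width at n = 10 is t(0.975, 9)/√10 = 0.72 SD of the change. It is useful beside the pre-post change but weak by itself.

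**The case against.** The strongest reply is that there is a second own-control contrast. A reader who stops halfway through the section 1 sentence might infer that the study has no internal control at all. The documents do not support that. On and off readings are taken at the same post assessment, so drift and regression to the mean largely drop out of their comparison. What remains is that this contrast speaks to the immediate effect of stimulation, whereas the primary objective concerns ES with training over a month. It is also unblinded, no test order is stated, and 7.2 plans only a correlation for it.

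Second, direction. A reader might infer that the bias favours the intervention. Practice would, but sections 1 and 1.1 describe slow worsening, and the MAS selection effect also points toward worsening. Selection is the weakest mechanism overall, because entry turns mainly on a fixed EDSS of 6.5.

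Third, safeguards exist: more than five years without relapse, three months of stable spasticity medication and dalfampridine, exclusion of recent chemodenervation, and enrolment only of people already optimised in rehabilitation. These limit real change. They do not address practice, rater or expectation effects.

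Fourth, a reader might infer that a ready-made untreated control month is being thrown away. That goes too far. The schema entry for screening may be a window, no gap to week 0 is fixed, and only the spasticity and task evaluations are listed at screening.

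Finally, this is a ten-person pilot with no power calculation, and a second reading cannot remove unblinded expectation or separate stimulation from training. All of that stands, and it is why the remedy below is descriptive.

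**Conclusion.** The point holds for the pre/post contrast, the only one for which 7.2 models an effect. That contrast has one pre-treatment reading, 6.1 allows it to be the screening value, and the single-group regression cannot separate treatment from retest, drift or selection. The sign of the net bias is not known.

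Its size cannot be taken from the documents. The 14% to 29% range is an illustration that depends on an assumed alpha of 5% and an assumed shift of 0.3 to 0.5 SD of the change score; the between-person figures also assume r. The MAS selection effect is small, about 0.1 SD at most under the assumptions used. The ambiguity about which reading is the baseline, and the treatment-effect label, rest on the text alone and need no assumption. The change is worth making because it is cheap; the point does not invalidate the pilot.

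**What to change.** 1. In 6.1, replace the sentence that allows screening data to serve as baseline with a rule that the scheduled outcomes, at least MAS and TUG, are always measured at week 0, and that week 0 is the baseline for all analyses.
2. In 6.1 and both schedule tables, keep the screening MAS as a separate earlier reading and add a short TUG at screening. MSQLI can be optional, because it is a longer battery. Record the date of each reading so that the interval is known.
3. In 7.2, report each participant's screening-to-week-0 change, with the mean change and its 95% CI, descriptively beside the pre-to-post change. Use no decision rule and do not average the two readings into the baseline. State that the untreated change is imprecise at n = 10, that a first-run TUG practice effect may exceed later ones, and that gait and voluntary movement are not covered.
4. In 7.2, call the estimate a pre-post change under ES plus training.

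Cost: protocol and SAP wording, slightly longer screening (including for people who then fail it), and no reuse of screening data to shorten week 0.
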